9/10/2019

NCT03095976 Unique Protocol ID: 1608175133

Principle Investigator: [name], DDS, MSD

Project title:

**Amnion-Chorion Allograft Barrier Used for Root Surface and Guided Tissue
Regeneration for Periodontal Intrabony Defects and Grade II Furcation
Defects.**

Protocol:

Patients who are referred to the Graduate Periodontics Clinic at Indiana University School of Dentistry for the treatment of severe chronic/aggressive periodontitis will be screened for possible participation in this study. Up to 20 subjects will be accepted into this study.

Written informed consent and authorization will be obtained from all participants and they will be given a copy of the signed informed consent documents.

The procedures listed below are all within standard care for a regenerative therapy around the teeth except the application of the membrane on the root surface prior to the bone grafting. No data collected for this study will be taken from sources outside of that already recorded for standard of care procedures.

Inclusion / Exclusion Criteria:

The following site inclusion criteria will be used:

- 1) ASA class I or II;
- 2) age ≥ 18 years old;
- 3) Non-smoker;
- 4) diagnosis of chronic or aggressive periodontitis previously treated with nonsurgical mechanical debridement;
- 5) patients have at least one two-wall intrabony defect in interproximal areas with radiographic evidence of an intrabony component of ≥ 4 mm, PPD ≥ 6 mm with 1-wall or 2-wall or combination of those defects or Glickman Grade II furcation involvement on buccal of mandibular or maxillary first or second molars without soft tissue exposure of furcation entrance;
- 6) tooth mobility Miller Grade ≤ 1 ;
- 7) more than 2mm of keratinized tissue with those selected teeth.

The following exclusion criteria will be used:

- 1) did not meet all inclusion criteria;
- 2) pregnancy or nursing woman;
- 3) subjects with active systemic or localized infection (exclude chronic periodontitis);
- 4) poor compliance or failure to maintain good oral hygiene as ascertained by the presence of full-mouth plaque score $\geq 20\%$;
- 5) restorations or caries on root surfaces or untreated endodontic infections;
- 6) participants received periodontal surgical treatment on the same site of this study within 2 years;
- 7) use of systemic or local antibiotics on the anticipated surgical sites during the past 3 months.

Clinical Measurements

A single calibrated examiner will perform clinical baseline and 6-month follow up measurements. O'Leary plaque score will be assessed. Six sites of each tooth of probing depth (PD), recession (REC) and clinical attachment level (CAL) will be recorded to the nearest millimeter with a University of North Carolina Probe (UNC Probe). For Glickman grade II furcation defects, in addition to the previous measurements, vertical probing pocket depth (VPD) and horizontal probing depth (HPD) will be measured.

Radiographic assessment will be performed with vertical bite-wing radiographs at baseline and 6-month post-surgical treatment. In order to maximize the standardization of the angulation of radiographs, bite registration will be taken prior to the first radiograph and utilized with beam-guiding device. It will be stored to be used post operatively. Sirona Dental Systems© with 7mA 60kV with 0.16s exposure time will be utilized for all radiographs. Digital #2 films manufactured by Air Techniques Inc. will be used for radiographic assessment. Bony defect (BD) will be defined as the most coronal point where the periodontal ligament space showed a continuous width. If several bony contours could be identified, the most apical one that crossed the root will be defined as the BD and the most coronal one as alveolar crest. If the cemento-enamel junction (CEJ) was destroyed by the restorative treatment, the margin of the restoration will be taken as a landmark.

Surgical Procedures:

All surgery will be rendered at the Graduate Periodontics Clinic at Indiana University School of Dentistry. All the patients will be treated under local anesthesia (2% lidocaine with 1/100,000epi or 4% articaine with 1/100,000epi). If the patient is willing to receive the surgery under intravenous or oral sedation, those services will be provided based on the necessity. After local anesthesia, intracrevicular incisions will be made and full-

thickness mucoperiosteal flaps will be raised both buccally and lingually; the surgeon will try to preserve the maximum extent of the marginal and interdental gingival tissue to obtain primary closure and membrane coverage. Vertical releasing incisions will only be used if necessary to gain access for defect debridement. The alveolar bone will be exposed at least 3 mm beyond the edges of the defect, and periosteal releasing incisions will be made to ensure complete membrane coverage at the time of suturing if necessary. All granulation tissue will be removed, the defects will be debrided, and the roots will be thoroughly scaled and root planed by hand instruments and ultrasonic devices. Following debridement, 17% EDTA solution with cotton pellet will be applied on the root surface for 2 minutes. After thorough irrigation with saline, BioXclude® (Amnion-Chorion Membrane: FDA Approved materials for intrabony defects) will be cut into two pieces. The amnion-chorion BioXclude membrane is regulated by the FDA under section 361 of the Public Health Service Act as a “Human cells, tissues, and cellular or tissue-based product” (HCT/P). The FDA does not require pre-market approval for these products like it would with drugs, biologics or devices. Therefore, this product will have no associated “investigational device exemption” (IDE) number. The FDA views using amnion chorion as a wound covering to aid in the healing of tissues throughout the body to be a “homologous use”. One goes to the root surface, and coronal portion of the membrane has to be >3mm coronal of CEJ. Once applied the membrane, one drop of saline will be applied to obtain better adaptation of membrane on the root surface. Bone substitutes 0.5cc (Particle size of 0.25-0.5mm of Corticocancellous, Maxxeus®) will be hydrated for at least 10min prior to application, and applied into the defects. The bone particles will not exceed the edge of defects in order to avoid over fill. Following the bone graft will be delivered to the defect. The coronal portion of excessive membrane will be just folded over the graft materials. The other BioXclude membrane will be utilized over the grafts, and will always be placed coronal to the interproximal bone crest so that it completely covers the defect and extends 2 to 3 mm beyond the residual bone. No sutures, pins, or tacks will be used for membrane fixation or stabilization. The orientation of the membrane will not matter. Vertical or horizontal mattress sutures with 5-0 Prolene (Monofilament/Nylon) will be placed in the interproximal tissues to obtain primary closure as much as possible.

Intra-surgical Clinical Measurements.

Intrabony defects: defect morphology will be measured (1 wall, 2 walls and/or those combinations) from the deepest aspect of the defect from the most coronal side of edge of the defects.

Postoperative Care and Maintenance:

All patients will receive antibiotics (875mg amoxicillin twice /day) for one week. If participants are allergic to amoxicillin, clindamycin (150mg twice/day) for one week will be prescribed. Analgesics (600mg ibuprofen three times/day) will be prescribed as needed for discomfort. Pt will be seen one, two and four weeks as a post-operative follow up. Patients will be advised to rinse twice daily with 0.12% chlorhexidine for 2 weeks after surgery. Patients will be instructed to refrain from brushing the teeth in the surgical area for 2 weeks. After that, they will be instructed to initiate brushing with an extra-soft toothbrush. Subjects will be recalled at 4-week intervals after 4weeks from surgical procedure for a period of 6 months for plaque scoring, oral hygiene instruction, and professional prophylaxis as needed. No subgingival probing or instrumentation will be performed at the experimental sites until the 6-month follow-up appointment.

Statistical Analysis:

Due to the nature of this pilot study, no sample size justification estimated were performed. Means and standard deviations for all parameters will be calculated. The paired-sample t test will be used to assess the statistical significance of the difference between the initial and the 6-month visit within group. Difference will be considered statistically significant at the $P < .05$. All data analysis will be performed using statistical software. (Microsoft Excel.)

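### No healing complication is a study outcome, so early or individual adverse events go uncounted although visits that could record them are already scheduled

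*Combined protocol and SAP*

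**What the plan says.** All references are to the Combined protocol and SAP.

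- **Protocol (opening section).** One step departs from standard care: the procedures are routine "except the application of the membrane on the root surface prior to the bone grafting". The sample is a ceiling, not a target: "Up to 20 subjects will be accepted into this study". Study data are limited by source: "No data collected for this study will be taken from sources outside of that already recorded for standard of care procedures".
- **Clinical Measurements.** Besides the plaque score, "Six sites of each tooth of probing depth (PD), recession (REC) and clinical attachment level (CAL) will be recorded to the nearest millimeter". For furcation defects, "vertical probing pocket depth (VPD) and horizontal probing depth (HPD) will be measured". Radiographs supply bone-level landmarks. The examiner's measurements and the radiographs are taken at baseline and 6 months.
- **Surgical Procedures.** Releasing incisions are allowed where needed so that the membrane is fully covered, and the membrane itself is not fixed. The closing sutures "will be placed in the interproximal tissues to obtain primary closure as much as possible".
- **Intra-surgical Clinical Measurements.** Defect morphology is recorded at operation.
- **Postoperative Care and Maintenance.** "Pt will be seen one, two and four weeks as a post-operative follow up". Nothing is listed for assessment at these visits. Later recalls, every four weeks to 6 months, are for plaque scores, hygiene advice and cleaning. The treated sites are not probed before 6 months.
- **Statistical Analysis.** "Means and standard deviations for all parameters will be calculated", followed by a paired t test of the initial visit against 6 months. No counts or proportions are planned, and no rule is given for missing pairs.

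**The concern.** The reason for the study is a new placement of the membrane. For a pilot of a new placement, a basic question is how the wounds healed: whether the membrane or graft became exposed, the flap opened, the site became infected or the tooth was lost. The protocol treats closure and coverage as something the surgeon works for but may not fully achieve, yet whether coverage held is never a study observation.

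The planned outcomes do not fill the gap. They are read at 6 months and summarised as group means, so they do not show which patient had an early problem or when. A patient who loses the study tooth has no 6-month value and drops out of the paired comparison, and nothing in the plan requires the reason to be given. The report could then present mean changes and P values with no statement about complications. Early healing is also hard to reconstruct later if it was not noted at the time.

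**Working it through.** **Step 1. Is a complication recorded anywhere?** The plan contains no complication figure to reproduce, so this step is a reading of the text.

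| Contact | What the plan names | Complication named? |
|---|---|---|
| Baseline | Plaque, PD, REC, CAL, VPD/HPD for furcations, radiograph | No |
| Surgery | Defect morphology | No |
| Weeks 1, 2, 4 | Nothing | No |
| Four-weekly recalls | Plaque score, hygiene advice, cleaning | No |
| 6 months | As baseline | No |
| Analysis | Means, SDs, paired t tests | No |

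**Step 2. Could the planned analysis show an event indirectly?** In part. PD, REC, CAL, VPD, HPD and bone level can all worsen, and the t test is of a difference, not of an improvement. But with 20 patients, and one value per patient assumed, each patient carries 1/20 = 5% of the mean, so a single bad result is diluted. An early event that had resolved by 6 months need leave no trace. A lost tooth removes a pair: 20 pairs become 19, and degrees of freedom go from 19 to 18. The fall in n would be visible, but the reason would not.

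**Step 3. What would counting deliver?** Inputs: n is at most 20 (opening section). The documents give no event rate, so 5%, 10% and 15% are assumptions. Every event is assumed to be detected, and patients are counted once.

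- Chance of seeing at least one event: 1 − (1 − p)^n. For n = 20 and p = 0.05, this is 1 − 0.95^20 = 0.642.
- Exact (Clopper-Pearson) two-sided 95% upper limit with no events: 1 − 0.025^(1/n). For n = 20 this is 0.168.

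| n | p = 5% | p = 10% | p = 15% | Upper limit if 0/n |
|---|---|---|---|---|
| 10 | 40% | 65% | 80% | 30.8% |
| 15 | 54% | 79% | 91% | 21.8% |
| 20 | 64% | 88% | 96% | 16.8% |

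The middle columns are the chance of at least one event. With events observed at n = 20, the exact 95% intervals are 0.1% to 24.9% for 1/20 and 1.2% to 31.7% for 2/20.

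If complications occur at these rates, a pilot of this size would more likely than not meet at least one, except at 5% with only 10 patients. Even a clean record would leave a wide upper limit.

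**The case against.** **The plan can show harm.** This stands. A reader might infer that the pilot can report benefit but never harm. The text does not support that: recession, attachment loss and bone loss are measured, and the test is of change in either direction. The gap is limited to early and individual events.

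**Clinic notes may already hold complications.** This stands in part. Study data come from standard-care records, and weeks 1, 2 and 4 are post-operative visits, so it cannot be said that complications will never be written down anywhere. But the plan does not say they will be extracted or tabulated. The consent pages are not available; a list of risks there would not make a complication a study outcome.

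**Closure is not treated as casually as one phrase suggests.** This is fair. Surgical Procedures also provides for full membrane coverage at suturing. That describes the intention at operation; it does not record whether coverage lasted.

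**Counts would not answer the question about the root-surface step.** This stands. Exposure, dehiscence or infection could arise from the flap, the graft or the second membrane over the graft. No control arm is described and no acceptable rate is stated, so the counts describe the whole procedure and cannot show that the new step is safe. The same limit applies to attributing improvement to it.

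**Comparing CAL change by exposure status would be weak.** This stands. Two exposures in 20 would set two patients against eighteen.

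**Conclusion.** The point holds in a limited form. No complication is defined, recorded or analysed as a study outcome, although the protocol identifies one non-standard step and already schedules visits at 1, 2 and 4 weeks. Average deterioration at 6 months could be detected; early or individual events would not be counted, and a lost tooth would leave the paired test unexplained.

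This is an inexpensive improvement in reporting. It does not contradict the text or invalidate any planned analysis. The gain is modest: with no events, the two-sided 95% upper limit would run from 30.8% (10 patients) to 16.8% (20 patients). The detection probabilities rest on assumed rates of 5% to 15% and on complete detection. It would go too far to conclude that the added counts would establish safety, or that any event could be traced to the root-surface membrane.

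**What to change.** 1. **Postoperative Care and Maintenance.** At the 1-, 2- and 4-week visits and at 6 months, record yes/no for membrane or graft exposure, flap dehiscence, infection at the site, and loss of the study tooth. Give each a one-line definition and say who records it, since the calibrated examiner is assigned only the baseline and 6-month measurements.
2. **Data source.** Draw these items from routine post-operative notes, so that the opening section's limit to standard-care data is respected. If the notes do not cover them, amend that sentence.
3. **Statistical Analysis.** Report the number of patients with each event out of all treated patients, with an exact 95% CI. State the number of patients missing from each paired test and the reason for each.
4. **Interpretation.** State that the limits are coarse, using the number actually treated, and that with no control arm described events cannot be attributed to the root-surface membrane.
5. **No subgroup test.** Do not compare CAL change by exposure status. If it is of interest, list the affected patients individually.

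The cost is four yes/no items at visits already planned, one descriptive table and slightly more data entry, with no added visit or procedure. If the notes prove insufficient, there is also one sentence to amend.

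### Does the plan need changing because its only test, against baseline, cannot isolate the root-surface membrane?

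*Combined protocol and SAP*

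**What the plan says.** The opening Protocol section describes the listed procedures as "all within standard care for a regenerative therapy around the teeth except the application of the membrane on the root surface", so one step is experimental. It also caps enrolment: "Up to 20 subjects will be accepted into this study". No arms, allocation, split-mouth comparison or historical comparator are described.

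Surgical Procedures sets out a single operation: debridement, root planing, EDTA conditioning, one piece of membrane on the root, bone graft, and then a second piece, since "The other BioXclude membrane will be utilized over the grafts". Postoperative Care and Maintenance adds more for everyone. "All patients will receive antibiotics" is one example; chlorhexidine rinsing and recall every four weeks are others.

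Clinical Measurements adds two outcomes for Grade II furcations only: "vertical probing pocket depth (VPD) and horizontal probing depth (HPD) will be measured".

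Statistical Analysis calls the study a pilot and gives no sample size calculation. It then says "Means and standard deviations for all parameters will be calculated", and names one test: "The paired-sample t test will be used to assess the statistical significance of the difference between the initial and the 6-month visit within group". The significance sentence begins "Difference will be considered statistically significant at the" and sets the threshold at P < .05. Sidedness is not stated.

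**The concern.** The one step that is not standard care is given to every patient together with everything else. Its effect cannot be separated from that of debridement, grafting, the second membrane piece, antibiotics, hygiene recall and the passage of time. Entry on a probing depth of at least 6 mm also leaves room for regression to the mean. The null hypothesis of the planned test is no change from baseline. It is not that the root-surface piece adds nothing.

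If a reader took P < .05 as evidence for the root-surface piece, the conclusion would have no support, and more patients would not help. The plan asks for no confidence interval on the change and has no sentence limiting what a significant result means. Enrolment has no stated minimum, and the furcation-only outcomes may rest on few patients, so some estimates could be imprecise.

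**Working it through.** The plan states no power, expected change or SD, so there is no figure of its own to reproduce. The main question is settled by reading; the arithmetic only illustrates it.

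**1. Is the added effect identifiable?** Only one operation is described, and it includes the root-surface piece. The phrase about testing within group might refer to intrabony and furcation defects, but neither would be a group treated without that piece. The added effect is not identifiable.

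**2. What does the test do if the root-surface piece adds nothing?** Let d be the mean change due to everything else, divided by the SD of the change. Assumptions: two-sided 0.05, one pair of values per patient, normal changes.

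Power = P(|T| > t(.975, n−1)), where T is noncentral t with n−1 degrees of freedom and noncentrality d√n. For n = 20 and d = 1, the noncentrality is √20 = 4.47, the critical value is 2.093 and the power is 0.99 (simulation of 100,000 trials: 0.989).

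| d (assumed) | n = 20 | n = 10 |
|---|---|---|
| 0 | 0.05 | 0.05 |
| 0.5 | 0.56 | 0.29 |
| 0.75 | 0.89 | 0.56 |
| 1.0 | 0.99 | 0.80 |

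The probability runs from 5% to nearly 100% depending on d and n, neither of which the documents fix. The table confirms the logic of step 1; it does not measure a fault in this trial.

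**3. Is the test sound for its own question?** Yes. At d = 0 it rejects 5% of the time. With 20 patients it has 80% power for a true change of 0.66 SD, so a null result at full enrolment would also say something about change from baseline.

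**4. Would a confidence interval help?** Its half-width is t(.975, n−1)/√n in units of the SD of change: 2.093/4.472 = 0.47 at n = 20 and 2.262/3.162 = 0.72 at n = 10. This describes precision. The interval is centred on the same mean change, so it is exactly as confounded as the P value. With complete pairs, the mean change is the difference of the two planned means. If t or an exact P is reported, the standard error follows as mean change divided by t, and the interval from that.

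**5. Would a control group within 20 patients help?** With 10 per arm the comparison would address attribution. The difference detectable with 80% power is 1.32 SD by noncentral t, or (1.960 + 0.842) × √(2/10) = 1.25 SD by the normal approximation. Power for a 0.5 SD difference would be 18.5%. By the normal approximation, 80% power for 0.5 SD needs 63 per arm.

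**The case for a change.** The best argument for changing the plan is that the change is cheap and the misreading foreseeable. The title puts the root-surface use first, the Protocol section singles that step out, and nothing limits the conclusion. A pilot is chiefly useful for an estimate and its precision, yet the plan uses pilot status to omit a sample size calculation while keeping a significance threshold. The planned means and standard deviations need not include the SD of the within-patient change. Baseline and 6-month SDs do not yield that without the correlation, and a bare P < .05 would not let a reader recover it.

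Part of this stands. The added effect cannot be estimated, and reporting the mean change with its SD, interval and number of patients would be good practice. The rest does not make a case for amendment. The title names both uses of the barrier together, which fits a study of the combined procedure. The threshold only defines when a difference is called significant; no claim of efficacy and no decision to proceed depends on it. A limiting sentence would disclaim an inference the plan never draws, and an interval leaves attribution where it was. Low enrolment and few furcation cases are possible, but the documents give no figure for either, and they bear on precision, not attribution.

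**Conclusion.** No change is called for. Followed as written, the plan gives a valid statement about change from baseline to 6 months after the combined procedure, and that is all it sets out to test. It cannot estimate the added effect of the root-surface piece at any sample size, and it does not claim to. A control group within the 20-patient ceiling would have 80% power only for differences of about 1.3 SD, so the uncontrolled design is a fair trade-off for a pilot. An interval or a cautionary sentence is a reporting choice the authors can make without altering the plan, and neither would correct a wrong result.

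This rests on three things: the documents state no objective or hypothesis about the root-surface piece alone; all patients receive the procedure as described; and each patient contributes one baseline and 6-month pair per test. The values of d and the two-sided level are assumptions, and the conclusion does not depend on them. If a report later credited the change to the root-surface piece, the fault would lie in that report.
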